#### **6.2 Analysis methods**

As this is a feasibility study no statistical analysis will be undertaken. Note that the intracluster correlation (ICC) between allocated shock groups will be calculated for consideration in future studies.

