#### 3. STUDY METHODS

## 3.1 Trial design

POSED is a single-centre, cluster-randomised multi-arm study. Defibrillators will be randomised to deliver one of three shock strategies:

Group	First shock	Second shock	Subsequent shocks	Strategy
1	120	150	200	Escalating
2	150	200	200	Escalating
3	200	200	200	Fixed

These three shock strategies represent current standard of care in UK Ambulance Services.

This feasibility study aims to recruit 90 patients, ideally 30 in each arm.

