#### 3.2 Randomisation

POSED is a cluster randomised study and the unit of randomisation is the defibrillator. Defibrillators will be allocated to one of the three treatment groups in a 1: 1: 1 ratio using simple randomisation. The randomisation will be stratified by ambulance station and by vehicle type (ambulance/response car/team leader vehicle).

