#### 3.3 Sample size

This feasibility study aims to recruit 90 patients, ideally 30 in each arm. It is popularly believed that a sample size should be at least 30, based on the central limit theorem whereby as a population becomes large it achieves an approximately normal distribution. (4) Although these is no statistical proof that 30 is a 'large' number in this context, my sample size of 30 in each treatment arm will be sufficiently large to inform discussion around secondary outcomes whilst allowing for missing data and loss to follow up.

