#### 3.4 Framework

This is a feasibility study and as such is not testing statistical hypotheses.

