#### 4. STATISTICAL PRINCIPLES

#### 4.1 Confidence intervals and P values

There will not be a formal statistical analysis as the study has not been powered to assess difference in interventions. The analyses will be based on summary statistics, namely mean, standard deviation, median, interquartile ranges and missingness in the data. Where possible 95% confidence intervals will also be given.

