#### 6.6 Statistical software

No statistical software is required.

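### SAP 6.2 defines the ICC across the three treatment arms, but the randomised cluster is the defibrillator, so the figure as written cannot feed a design effect

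*SAP*

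**What the plan says.** Section 3.1 describes the design: "POSED is a single-centre, cluster-randomised multi-arm study. Defibrillators will be randomised to deliver one of three shock strategies". The three strategies are listed there as groups 1 to 3. Section 3.2 names the cluster: "POSED is a cluster randomised study and the unit of randomisation is the defibrillator". It then gives the allocation: "Defibrillators will be allocated to one of the three treatment groups in a 1: 1: 1 ratio using simple randomisation".

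Section 6.2 states that no statistical analysis is planned, and adds one exception: "Note that the intracluster correlation (ICC) between allocated shock groups will be calculated for consideration in future studies". It names no outcome, estimator or interval for this ICC, and no section of the SAP defines an ICC for patients sharing a defibrillator.

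On size, section 3.3 says "This feasibility study aims to recruit 90 patients, ideally 30 in each arm". The SAP gives no number of defibrillators, no expected number of patients per defibrillator, no event rate and no anticipated ICC.

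**The concern.** An ICC is worth reporting from a cluster-randomised feasibility study because a later trial uses it in the design effect, 1 + (m − 1) × ICC, where m is the number of patients per cluster. That formula needs the correlation between patients in the same randomised cluster, which here is the defibrillator.

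Section 6.2 instead points to the groups to which defibrillators are allocated, and those are the arms. Arm is a fixed treatment factor with three levels. Variance between arms is treatment effect plus noise, on 3 − 1 = 2 degrees of freedom. An analyst who followed the sentence literally would obtain a number near zero when the arms perform alike, however strong the clustering by device. The number would be positive when the arms differ, even with no clustering at all. It would then pass to the main trial's designers under the label of an ICC. This is the only clustering parameter that the study hands forward.

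**Working it through.** **1. The plan's own figure.** 3 arms × 30 patients = 90, as section 3.3 states. There is no stated ICC or design effect to reproduce.

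**2. Inputs.** From the SAP: 90 patients, 30 per arm, three arms, defibrillator as cluster. Assumed, because the SAP is silent: 45 devices (15 per arm), with each patient equally likely to meet any device in the arm; a 20% event rate; true device ICC of 0.05 or 0.20; and, for the case without clustering, arm event rates of 10%, 20% and 35%.

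**3. What the arm-based ICC measures when arms are equal.** Two patients in the same arm share a device with probability 1/15. Their correlation is therefore the device ICC divided by 15:
- device ICC 0.05: 0.05 / 15 = 0.0033
- device ICC 0.20: 0.20 / 15 = 0.0133

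Simulation with beta-binomial device effects and the one-way ANOVA estimator (4,000 data sets per scenario) gave averages of about 0.003 and 0.013. The device-level estimator, nested within arm, averaged about 0.05 and 0.20 on the same data. The arm-based figure misses the clustering that is there.

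**4. What it measures when arms differ and there is no clustering.** Arm rates 0.10, 0.20 and 0.35 have mean 0.2167.
- Between-arm variance: (0.0136 + 0.0003 + 0.0178) / 2 = 0.0158
- Mean within-arm variance: (0.0900 + 0.1600 + 0.2275) / 3 = 0.1592
- Ratio: 0.0158 / (0.0158 + 0.1592) = 0.09

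Simulation gave 0.083 to 0.087 across separate runs; the device-level estimator averaged about 0. Here the arm-based figure reports clustering that does not exist.

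**5. Sensitivity to the assumptions.** With 30, 60 or 90 devices, equal arm rates of 30% and a true device ICC of 0.20, the arm-based figure averaged 0.019, 0.009 and 0.006. With no clustering and arm rates of 20%, 30% and 50%, it averaged about 0.10. The pattern does not depend on the choice of 45 devices or 20%.

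**6. Consequence for a later trial, if it used 0.003 when the truth is 0.05.**

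| Patients per cluster (assumed) | Design effect at 0.05 | Design effect at 0.003 | Ratio |
|---|---|---|---|
| 2 | 1.050 | 1.003 | 1.05 |
| 3 | 1.100 | 1.006 | 1.09 |
| 10 | 1.450 | 1.027 | 1.41 |

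**7. Precision of the right quantity.** With a true device ICC of 0.05, 45 devices and a 20% event rate, 95% of device-level estimates fell between about −0.2 and 0.35. With 30 devices the range was about −0.16 to 0.30, and with 90 devices about −0.37 to 0.45.

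**The case against.** The best reply is that this is a slip of the pen. The sentence uses the word intracluster, section 3.2 names the cluster, and a trial statistician might well compute the device-level ICC regardless. That is plausible, and the point does not rest on any intention to treat arms as clusters. But no other part of the SAP supplies the correct reading, and the text as it stands leads to a different number.

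The second reply is that little depends on it. This stands in part. A reader might infer that the ICC is the only planning parameter the study offers. It is not: numbers eligible and recruited, adherence and data completeness (sections 2.2, 5.1 and 6.1) also inform the main trial, and the primary objective is untouched. A reader might also infer that the main trial will be mis-sized, by about 41%. The SAP does not support that. The ICC is offered only for consideration, no sizing rule depends on it, and 1.41 requires 10 patients per cluster, a value found nowhere in the document. At 2 per cluster, as in the 45-device scenario, the excess is about 5%.

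The third reply is that even the correct ICC would be too imprecise to size a trial on its own. That is true. It is a reason to report an interval and a caution, not to report a different quantity.

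Two neighbouring statements are secondary. Section 4.1 says "Where possible 95% confidence intervals will also be given" without mentioning clustering, and the statistical software section (6.6) says "No statistical software is required", which sits awkwardly with estimating any ICC. The plan is descriptive ("This is a feasibility study and as such is not testing statistical hypotheses"), so neither carries much weight alone.

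**Conclusion.** The point holds in a limited form. Section 6.2 contradicts section 3.2 on what the cluster is. Followed literally, it yields a between-arm quantity that cannot be used in a design effect for a trial that randomises defibrillators. That conclusion follows from the text and needs no assumed numbers.

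The size of the error does rest on assumptions. In the scenarios examined, the figure as written is about one fifteenth of the true device ICC when arms are equal, and about 0.09 with no clustering when arm rates are 10%, 20% and 35%. The planning consequence of using 0.003 for a true 0.05 runs from about 5% to about 41% more patients than planned over 2 to 10 patients per cluster. It arises only if a later team sizes its trial on this figure. The correction is worth making because it costs almost nothing, but it does not threaten the feasibility study's own objectives.

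**What to change.** Replace the ICC sentence in section 6.2 with wording such as:

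> The ICC for patients within the same defibrillator, adjusted for treatment arm, will be estimated for the main clinical outcomes in 6.1.2 and reported with a 95% CI, together with the number of defibrillators and the distribution of patients per defibrillator.

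Add that, with about 90 patients, the estimate will be imprecise and should not be used alone to size the main trial. The range of about −0.2 to 0.35 can be quoted, labelled as resting on assumed values (45 devices, 20% event rate, true ICC 0.05).

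As consequential tidying, name the estimator in 6.2 and the software in 6.6, and say in 4.1 whether the confidence intervals allow for clustering by defibrillator.

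The cost is a change of wording and minor programming. Allocation is by device, so the device identifier should already be held. The visible downside is a wide reported interval, which is a fair account of what 90 patients can show.

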## 6.3 Missing data

All reasonable attempts will be made to prevent missing data. Since this is a feasibility study, only the proportion of missing data will be reported. No imputation or other techniques will be employed to minimise the impact of missing data.

## 6.4 Additional analyses

No additional analysis is required.

#### 6.5 Harms

Few if any SAEs are expected since many of the criteria of an SAE are conditions normally associated with cardiac arrest or attempted resuscitation. Summary data for each SAE will be reported including information on severity, expectedness and causality.

## 6.6 Sub-groups

In relation to initial shock (VT/pVT) as our outcome, we will conduct sub-group analyses of:

- 1. Hospital handover (ROSC, CPR ongoing, not conveyed);
- 2. 30 days survival (died/alive);
- 3. Survival at discharge (died/alive).

We will assess the interaction of the treatment arm, with each of the sub-groups.

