# Neurological outcome at 30 days

	Group A	Group B	Group C	All cases
	(n= )	(n= )	(n= )	(n= )
mRS score at discharge – n (%)				
0	n (%)	n (%)	n (%)	n (%)
1	n (%)	n (%)	n (%)	n (%)
2	n (%)	n (%)	n (%)	n (%)
3	n (%)	n (%)	n (%)	n (%)
4	n (%)	n (%)	n (%)	n (%)
5	n (%)	n (%)	n (%)	n (%)
6	n (%)	n (%)	n (%)	n (%)
Missing	n (%)	n (%)	n (%)	n (%)
mRS score at 30 days – n (%)				
0	n (%)	n (%)	n (%)	n (%)
1	n (%)	n (%)	n (%)	n (%)
2	n (%)	n (%)	n (%)	n (%)
3	n (%)	n (%)	n (%)	n (%)
4	n (%)	n (%)	n (%)	n (%)
5	n (%)	n (%)	n (%)	n (%)
6	n (%)	n (%)	n (%)	n (%)
Missing	n (%)	n (%)	n (%)	n (%)
Neurological outcome - n (%)				
Good (mRS ≤ 3)	n (%)	n (%)	n (%)	n (%)
Death/poor (mRS = 4-6)	n (%)	n (%)	n (%)	n (%)
Missing	n (%)	n (%)	n (%)	n (%)

Sub-group analysis: Neurological outcome of patients with initially shockable rhythm (VF/pVT)

	Group A	Group B	Group C	All cases
	(n=)	(n= )	(n= )	(n= )
mRS score at discharge – n (%)				
0	n (%)	n (%)	n (%)	n (%)
1	n (%)	n (%)	n (%)	n (%)
2	n (%)	n (%)	n (%)	n (%)
3	n (%)	n (%)	n (%)	n (%)
4	n (%)	n (%)	n (%)	n (%)
5	n (%)	n (%)	n (%)	n (%)
6	n (%)	n (%)	n (%)	n (%)
Missing	n (%)	n (%)	n (%)	n (%)
mRS score at 30 days – n (%)				
0	n (%)	n (%)	n (%)	n (%)
1	n (%)	n (%)	n (%)	n (%)
2	n (%)	n (%)	n (%)	n (%)
3	n (%)	n (%)	n (%)	n (%)
4	n (%)	n (%)	n (%)	n (%)
5	n (%)	n (%)	n (%)	n (%)
6	n (%)	n (%)	n (%)	n (%)
Missing	n (%)	n (%)	n (%)	n (%)
Neurological outcome - n (%)				
Good (mRS ≤ 3)	n (%)	n (%)	n (%)	n (%)
Death/poor (mRS = 4-6)	n (%)	n (%)	n (%)	n (%)
Missing	n (%)	n (%)	n (%)	n (%)

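### SAP 6.6 Sub-groups swaps outcome and sub-group, contradicts the SAP's own table shells, and promises an interaction assessment that other sections exclude

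*SAP*

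**What the plan says.** Two sections of the SAP carry the number 6.6. This point concerns 6.6 Sub-groups.

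- **Outcome and sub-groups.** The section begins "In relation to initial shock (VT/pVT) as our outcome, we will conduct sub-group analyses of" and lists three items: status at hospital handover (three levels), 30-day survival and survival at discharge (two levels each).
- **Interaction.** It ends "We will assess the interaction of the treatment arm, with each of the sub-groups". It gives no model, scale or allowance for the defibrillator as the randomised cluster.
- **Framework.** Section 3.4 states "This is a feasibility study and as such is not testing statistical hypotheses". Section 4.1 limits the analyses to summary statistics, with 95% confidence intervals where possible, because the study is not powered for differences between arms. Section 6.2 states "As this is a feasibility study no statistical analysis will be undertaken", with an intracluster correlation as its one exception. Section 6.6 Statistical software says that none is needed.
- **Shells.** Section 7 has sub-group versions of the out-of-hospital, electrical and neurological outcome tables. The last is titled "Sub-group analysis: Neurological outcome of patients with initially shockable rhythm (VF/pVT", and the other two use the same sub-group. The Survival table has no such version.

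**The concern.** A sub-group analysis compares arms on an outcome within groups fixed before treatment could act. Section 6.6 Sub-groups has this the wrong way round. It forms groups from what happened to patients after they were shocked, and it names as the outcome something tied to the initial shock or rhythm.

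The text and the shells therefore ask for different tables, and a programmer cannot follow both. The interaction sentence is also the only place where the SAP promises a between-arm comparison that goes beyond description. An interaction listed in advance could be given weight in planning the main trial, although the rest of the SAP says that the study is not built to compare the arms.

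**Working it through.** **1. How the SAP classifies each variable elsewhere**

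| Item | Role in 6.6 Sub-groups | Role elsewhere |
|---|---|---|
| Initial rhythm, if that is what is meant | Outcome | Baseline characteristic (5.5); sub-group in three section 7 shells |
| Status at hospital handover | Sub-group | ROSC at handover is a clinical outcome (6.1.2); row of the Survival shell |
| Survival at discharge | Sub-group | Clinical outcome (6.1.2); row of the Survival shell |
| 30-day survival | Sub-group | Part of the 30-day clinical outcome (6.1.2); row of the Survival shell |

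**2. What the named outcome could mean**

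- *Presenting rhythm.* It exists before any shock, so the allocated energy cannot change it. Any difference between arms reflects chance or the selection caused by splitting on survival.
- *Rhythm after the first shock.* The Electrical outcomes shell tabulates this with VF and pVT rows, and energy can affect it. The groups are still defined by later survival, which energy may also affect, so arms within a group are no longer comparable by randomisation.
- *A restriction to VF/pVT patients.* The outcome is then the same for everyone and there is nothing to compare.

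No reading gives a usable treatment comparison. The label VT/pVT also appears only here; the baseline list and the shells use VF/pVT.

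**3. Text against shells**

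The three items in 6.6 Sub-groups are exactly the three blocks of the Survival shell, and that shell lacks a VF/pVT version. Conversely, the text does not call for the electrical and neurological sub-group shells.

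**4. How precise an interaction could be**

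The plan's own figure: "This feasibility study aims to recruit 90 patients, ideally 30 in each arm". Three arms of 30 give 3 × 30 = 90, as stated. The SAP gives no rhythm mix and no survival rate, so the rates below are assumptions. Clustering is ignored.

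For two arms with the same expected counts in the four rhythm-by-survival cells a, b, c and d, the standard error of the log ratio of odds ratios is

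SE = √[2 × (1/a + 1/b + 1/c + 1/d)],

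and the 95% interval multiplies and divides the estimate by exp(1.96 × SE). An odds ratio is symmetric, so the result is the same whichever of presenting rhythm and survival is called the outcome.

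- *Best case tried:* 50% shockable, 50% survival in both rhythm groups. Each cell is 30 × 0.5 × 0.5 = 7.5. SE = √(2 × 4/7.5) = 1.03. Factor = exp(1.96 × 1.03) ≈ 7.6.
- *More typical case:* 70% shockable, survival 30% if shockable and 10% if not. Cells are 6.3, 14.7, 0.9 and 8.1. SE = √[2 × (0.159 + 0.068 + 1.111 + 0.123)] = √2.92 = 1.71. Factor ≈ 28.

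| Shockable | Survival, shockable / not | SE | 95% CI factor (× or ÷) | Ratio detectable with 80% power (two-sided 5% assumed) |
|---|---|---|---|---|
| 50% | 50% / 50% | 1.03 | 7.6 | 18 |
| 70% | 30% / 30% | 1.23 | 11.1 | 31 |
| 50% | 30% / 10% | 1.45 | 17.3 | 59 |
| 70% | 30% / 10% | 1.71 | 28.5 | 120 |
| 80% | 30% / 10% | 2.02 | 52.9 | 291 |

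**5. Could the interaction be fitted at all?**

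An empty arm-by-rhythm-by-survival cell makes an ordinary interaction contrast infinite or undefined. In simulation with 30 per arm, the chance of at least one empty cell was 78% at 70% shockable with 30%/10% survival, 17% at 70% with 30%/30%, and 5% at 50% with 30%/30%. Over all rates tried (50–90% shockable, 5–40% survival) it ran from about 1% to over 99%.

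**The case against.** The strongest reply is that this is poor wording with little consequence. The shells show what was probably meant, VT/pVT looks like a typing slip, and the primary outcome (proportion of eligible patients randomised) and the secondary outcomes (adherence and data completeness) do not use this section. That stands, and it limits how serious the point is. It does not make the text executable, because text and shells still call for different tables.

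A second reply is that the section speaks of an initial shock, not an initial rhythm. It is then too strong to say flatly that energy cannot affect the outcome. That also stands: the argument holds for the presenting rhythm but not for the rhythm after the first shock. Grouping by later survival is wrong on both readings.

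A third is that the section says interactions will be assessed, not tested, so 3.4 may not be breached. Section 6.4 ("No additional analysis is required") is also weak evidence, since it need not govern a separately numbered section. Both are fair. The conflict rests mainly on 4.1 (summary statistics only), on 6.2 and on the statement that no software is needed.

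A reader might go further in three ways that the document does not support:

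- *That the interactions mostly could not be estimated.* With 25% non-shockable and 5% survival among them, the chance that an arm has no non-shockable survivor is (1 − 0.0125)^30 = 0.686, so the chance that at least one of three arms has none is 1 − (1 − 0.686)³ = 0.97. Those rates are assumed, and the wider range in the working runs from about 1% to over 99%. The calculation also leaves out handover status.
- *That three tests carry a 14% false-positive risk.* The figure 1 − 0.95³ = 0.143 needs a 5% level and independent tests. The SAP sets no significance level.
- *That the SAP rules out all sub-group work.* Only the interaction conflicts with other sections. The descriptive VF/pVT tables are planned.

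**Conclusion.** The section is wrong as written and should be corrected. Three findings rest on the SAP alone: outcome and sub-group are reversed, the text does not match the shells, and the interaction does not fit 3.4, 4.1, 6.2 and 6.6 Statistical software.

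The statement about precision rests on assumed rates, 30 patients per arm and no allowance for clustering. On that basis the 95% interval on a ratio of odds ratios spans a factor of about 8 either way in the best case tried, about 28 in the more typical case, and more if fewer patients have a non-shockable rhythm. Too imprecise to inform is the right description; impossible to estimate is not shown.

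This is a should-fix. The feasibility conclusions do not depend on it.

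**What to change.** Replace the content of 6.6 Sub-groups with wording such as:

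> Sub-group: patients with initially shockable rhythm (VF/pVT). Handover status, survival at discharge, 30-day survival, out-of-hospital outcome, electrical outcomes and mRS are summarised by arm as n (%), with 95% CI where possible. Time to prehospital ROSC is summarised as in its shell.

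In addition:

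- Correct VT/pVT to VF/pVT, and refer to initial rhythm, not initial shock.
- Add the VF/pVT version of the Survival table to section 7.
- Delete the interaction sentence, so that the section agrees with 3.4, 4.1, 6.2 and 6.6 Statistical software.

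The cost is one paragraph and one table shell, with no new data. What is lost is an interaction assessment that could not have informed the main trial. Separate tables for PEA/asystole are not needed; the SAP does not plan them and their cells would be very small.

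If the sponsor wants to keep an interaction, the costlier route is to turn it the right way round, specify a model and scale that allow for defibrillator clustering, label it exploratory, and amend the four conflicting sections.

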#### 6.6 Statistical software

No statistical software is required.

# 7. TEMPLATE TABLES

# **Baseline characteristics**

	Group A	Group B	Group C	All cases
	(n= )	(n= )	(n= )	(n= )
Age – N				
Mean	μ	μ	μ	μ
SD	σ	σ	σ	σ
Median (IQR)	Median (Q1:Q3)	Median (Q1:Q3)	Median (Q1:Q3)	Median (Q1:Q3)
Missing - n (%)	n (%)	n (%)	n (%)	n (%)
Gender – n (%)				
Male	n (%)	n (%)	n (%)	n (%)
Female	n (%)	n (%)	n (%)	n (%)
Missing	n (%)	n (%)	n (%)	n (%)
Location of arrest - n (%)				
Private residence	n (%)	n (%)	n (%)	n (%)
Public place	n (%)	n (%)	n (%)	n (%)
Other	n (%)	n (%)	n (%)	n (%)
Missing	n (%)	n (%)	n (%)	n (%)
Witnessed event – n (%)				
Witnessed	n (%)	n (%)	n (%)	n (%)
Unwitnessed	n (%)	n (%)	n (%)	n (%)
Missing	n (%)	n (%)	n (%)	n (%)
Bystander CPR (B-CPR) – n (%)				
Non-EMS witnessed	n (%)	n (%)	n (%)	n (%)
events receiving B-CPR				
Missing	n (%)	n (%)	n (%)	n (%)
Prior shocks delivered by non-				
study defibrillator	n (%)	n (%)	n (%)	n (%)
Initial rhythm – n (%)				
VF/pVT	n (%)	n (%)	n (%)	n (%)
PEA	n (%)	n (%)	n (%)	n (%)
Asystole	n (%)	n (%)	n (%)	n (%)

Missing	n (%)	n (%)	n (%)	n (%)
Time from call to application of				
defibrillator – N				
Mean	μ	μ	μ	μ
SD	σ	σ	σ	σ
Median (IQR)	Median (Q1:Q3)	Median (Q1:Q3)	Median (Q1:Q3)	Median (Q1:Q3)
Missing - n (%)	n (%)	n (%)	n (%)	n (%)
Aetiology of cardiac arrest – n (%)				
Cardiac	n (%)	n (%)	n (%)	n (%)
Non-cardiac	n (%)	n (%)	n (%)	n (%)
Missing	n (%)	n (%)	n (%)	n (%)

